2.6.3 Multiplicity adjustment

A hierarchical testing strategy will be applied to control the family-wise type I error rate at the one-sided significance level of alpha=0.025 to assess superiority of inclisiran over placebo.

Novartis	For business use only	Page 27
SAP amendment 4		CKJX839C12301

Hypotheses associated with the key secondary endpoints will be tested in the order listed above in Section 2.6.1.

2.6.4 Sensitivity analyses

MMRM analysis using control-based pattern mixture model for missing value imputation will be performed for key secondary endpoints (except the time-adjusted percent change in LDL-C from baseline after Day 90 and up to Day 330) as specified for primary endpoint in Section 2.5.5. In model corresponding baseline value will be used instead of baseline LDL-C.

For the time-adjusted percent change in LDL-C from baseline after Day 90 and up to Day 330, mixed model for repeated measurements (MMRM) analysis without multiple imputation, that assumes missing data are MAR, will be performed. The model will be same as MMRM model mentioned in Section 2.6.2. A linear combination of the estimated means from visits Day 150, 270 and 330 will be used to compare treatment groups.

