8.3.1 LDL-cholesterol

The primary efficacy assessment will be LDL-C. Samples for LDL-C will be collected at screening and on Days 1, 90, 150, 270, 330, 360, 450, 510, 630 and 720 (Table 8-1).

After randomization (Day 1) until the Day 360 visit, the results from the LDL-C laboratory assessments must be blinded to participants, investigator staff, persons performing the assessments, and the CTT.

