2.5.5 Sensitivity analyses for primary endpoint/estimand

The following sensitivity analyses will be performed for the primary estimand, to assess the robustness of the estimation in the presence of deviations from the assumptions specified in the primary analysis on the FAS only:

Novartis	For business use only	Page 25
SAP amendment 4		CKJX839C12301

- Linear mixed-effect model for repeated measures (MMRM) analysis without multiple imputation
- MMRM analysis on the imputed datasets, and multiple imputation will be based on a control-based pattern mixture model
- ANCOVA using the washout model including the following fixed effects: baseline concomitant lipid-modifying therapies, baseline age group, region, and a treatment-by-region interaction.

Due to the limited sample size of some countries, pooled regions will be used as the fixed effect for ANCOVA model. Analyses using the MMRM will include fixed effects for treatment, baseline age group (\geq 12-<15 or \geq 15-<18 years of age), visits, interaction between treatment and visits, baseline LDL-C. Day 90, 150, 270, 330 and 360 will be included as visit. The Restricted Maximum Likelihood (REML) estimation approach will be used with covariance structure set as "Unstructured". If the model does not converge with unstructured covariance matrix, the compound symmetry covariance matrix will be used in the mixed model.

The control-based pattern mixture model, as specified in Section 5.7.2, will be used to further explore the possibility of missing data being missing not at random. This approach will utilize placebo data for monotone missing inclisiran treatment data. Same MMRM as specified above will be used on analyze the imputed datasets.

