2.6 Analysis of the key secondary objective

2.6.1 Key secondary endpoints

The following are key secondary efficacy endpoints:

- Time-adjusted percent change in LDL-C from baseline after Day 90 and up to Day 330 (Year 1), defined as the average of percent changes from baseline to day 150, 270, and 330.
- Absolute change in LDL-C from baseline to Day 330 (Year 1)
- Percent change in Apo B from baseline to Day 330 (Year 1)
- Percent change in Lp(a) from baseline to Day 330 (Year 1)
- Percent change in non-HDL-C from baseline to Day 330 (Year 1)
- Percent change in total cholesterol from baseline to Day 330 (Year 1)

Secondary estimands corresponding to key secondary efficacy endpoints are defined similarly to the primary estimand. These endpoints, and the corresponding summary measures, are listed

Novartis	For business use only	Page 26
SAP amendment 4		CKJX839C12301

below. Population, treatment of interest, endpoints, and intercurrent events are defined similarly as for the primary estimand.

- Endpoint: time-adjusted percent change in LDL-C from baseline after Day 90 and up to Day 330 (Year 1). Summary measure: difference between treatment groups in mean time-adjusted percent change in LDL-C from baseline after Day 90 and up to Day 330 (Year 1).
- Endpoint: absolute change in LDL-C from baseline to Day 330 (Year 1). Summary measure: difference between treatment groups in mean absolute change in LDL-C from baseline to Day 330 (Year 1).
- Endpoint: percent change in Apo B from baseline to Day 330 (Year 1). Summary measure: difference between treatment groups in mean percent change in Apo B from baseline to Day 330 (Year 1).
- Endpoint: percent change in Lp(a) from baseline to Day 330 (Year 1). Summary measure: difference between treatment groups in mean percent change in Lp(a) from baseline to Day 330 (Year 1).
- Endpoint: percent change in non-HDL-C from baseline to Day 330 (Year 1). Summary measure: difference between treatment groups in mean percent change in non-HDL-C from baseline to Day 330 (Year 1).
- Endpoint: percent change in total cholesterol from baseline to Day 330 (Year 1). Summary measure: difference between treatment groups in mean percent change in total cholesterol from baseline to Day 330 (Year 1).

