2.6.2 Statistical hypothesis, model, and method of analysis

The key secondary endpoints will be analyzed using the same ANCOVA with multiple imputation using wash-out model as mentioned for primary endpoint except the time-adjusted percent change in LDL-C from baseline after Day 90 and up to Day 330. In the model baseline LDL-C will be replaced by baseline of respective endpoint. The estimate and corresponding 2-sided 95% confidence intervals of mean difference between treatment groups will be calculated. P-value for hypothesis test for mean difference will also be provided.

The time-adjusted percent change in LDL-C from baseline after Day 90 and up to Day 330 will be estimated using MMRM model. MMRM analysis (using control-based pattern mixture model for missing value imputation) will be performed on the percentage change in LDL-C from baseline over visits (Day 150, 270, 330) as specified for primary endpoint on each of the 100 imputed dataset. Then, linear combinations of the estimated means from visits Day 150, 270 and 330 will be used to compare treatment effects in terms of time-adjusted percent change in LDL-C. Treatment effects from these 100 MMRM analyses will then be combined using Rubin's Method. The estimate and corresponding 2-sided 95% confidence intervals of mean difference between treatment groups will be calculated. P-value for hypothesis test for mean difference will also be provided.

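### The only sensitivity analysis named for the time-adjusted LDL-C endpoint appears to leave Days 90 and 360 out of its no-imputation MMRM, so dropout related to the Day 90 response can bias it, in either direction

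*SAP*

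**What the plan says.** The endpoint is the first key secondary in the testing order, "defined as the average of percent changes from baseline to day 150, 270, and 330" (SAP 2.6.1).

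- **Main analysis (SAP 2.6.2).** The data are first completed by the control-based pattern-mixture imputation of SAP 5.7.2, which uses baseline and Days 90, 150, 270, 330 and 360. An MMRM "will be performed on the percentage change in LDL-C from baseline over visits (Day 150, 270, 330) as specified for primary endpoint" is then fitted to each of the 100 completed datasets.
- **Sensitivity analysis (SAP 2.6.4).** The imputation is dropped and missing at random (MAR) is assumed. The text is "analysis without multiple imputation, that assumes missing data are MAR, will be performed. The model will be same as MMRM model mentioned in"; the section cited is 2.6.2. On the contrast, it says "A linear combination of the estimated means from visits Day 150, 270 and 330 will be used to compare treatment groups".
- **Primary endpoint's MMRM (SAP 2.5.5).** This one has five visits: "Day 90, 150, 270, 330 and 360 will be included as visit".
- **Data available (Protocol 8.3.1).** "Samples for LDL-C will be collected at screening and on Days 1, 90, 150, 270, 330, 360" and at later visits, so the Day 90 and Day 360 values exist.

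**The concern.** A three-visit MMRM does no harm on imputed data, because nothing is missing and the earlier visit has already informed the imputation. Without imputation, a likelihood-based MMRM can recover missing outcomes only through the outcomes and covariates it contains. If Days 90 and 360 are left out, a participant with no LDL-C at Days 150, 270 and 330 has no row in the model. MAR then has to hold given baseline LDL-C and age group alone for that participant, although a post-treatment LDL-C was measured.

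Two things are at stake. First, the sensitivity estimate can carry a bias that data already collected would remove. Second, a sensitivity analysis should change one thing. Here the missing-data assumption and the data used change together, so a gap between the two results could not be put down to the assumption. That second point holds whatever the size of the bias, and SAP 2.6.4 names no other sensitivity analysis for this endpoint.

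**Working it through.** The plan states no figure for this point, and the SDs and effect in its sample-size section are blacked out, so there is nothing of the plan's own to reproduce. The check has two parts.

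**1. Which data enter each model**

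| Analysis | Imputation | LDL-C visits that inform the result |
|---|---|---|
| Time-adjusted endpoint, main (2.6.2 with 5.7.2) | Control-based | 90, 150, 270, 330, 360 |
| Time-adjusted endpoint, sensitivity (2.6.4) | None | 150, 270, 330 |
| Primary endpoint, MMRM sensitivity (2.5.5) | None | 90, 150, 270, 330, 360 |

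Only the middle row loses information.

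**2. Size of the bias under assumed dropout**

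Inputs from the documents: 141 enrolled and 2:1 allocation (SAP 1.1). The true difference is set at -45 points, within the range of adult time-adjusted reductions of 44% to 54% (Protocol 4.2).

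Assumed inputs: SD of percent change 20 in both arms (20 to 30 examined), equal between-visit correlation 0.6 (0.4 to 0.8 examined), and dropout of 3%, 5%, 10% or 20% immediately after Day 90. Unless stated otherwise, the log-odds of leaving change by 1.5 per SD of the Day 90 percent change. Leavers have no later LDL-C.

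Let u be the standardised Day 90 residual in an arm, p the dropout rate, ρ the correlation and σ the SD. The three-visit model then reduces to an ANCOVA of the Day 150/270/330 average in those who stay, and

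bias in an arm's mean = ρ × σ × E(u | stay), where E(u | stay) = -[p / (1 - p)] × E(u | leave).

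Bias in the difference = inclisiran-arm bias minus placebo-arm bias. Negative means the inclisiran effect is overstated.

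Take dropout related to response in the inclisiran arm only, at 5%. Numerical integration of the logistic model gives E(u | leave) = 1.232, so the bias is 0.6 × 20 × (-0.05/0.95 × 1.232) = 12 × (-0.0648) = -0.78. Simulation with 1.5 million participants gives -0.75. At 3% and 10% the formula gives -0.49 and -1.46, and simulation gives -0.46 and -1.43.

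Simulated bias in the difference, three-visit model (SD 20, correlation 0.6):

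| Dropout pattern | 3% | 5% | 10% | 20% |
|---|---|---|---|---|
| Poor Day 90 responders leave, inclisiran arm only | -0.5 | -0.8 | -1.4 | -2.7 |
| Poor responders leave inclisiran, good ones leave placebo | -1.0 | -1.6 | -2.9 | -5.4 |
| Same function of absolute Day 90 change in both arms | +1.1 | +1.8 | +3.1 | +5.0 |
| Same within-arm dependence and rate in both arms | about 0 | about 0 | about 0 | about 0 |
| Completely at random | about 0 | about 0 | about 0 | about 0 |

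In the third row most leavers are on placebo. By integration, 5% overall corresponds to 0.8% of inclisiran and 13.4% of placebo participants. Over all SD and correlation settings, 5% dropout gives an absolute bias of 0.5 to 2.8 points in the first three patterns.

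**With Day 90 added as an outcome** and the contrast unchanged, the bias is zero within simulation error (at most 0.11 points) in every setting. In 3,000 trials of 141 (inclisiran-only pattern):

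- At 5% dropout, mean bias goes from -0.72 to +0.05, with empirical SE 3.21 and 3.17. About 7 participants (0.05 × 141) are left out of the three-visit model.
- At 10% dropout, mean bias goes from -1.52 to -0.05, with SE 3.28 and 3.16.

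The simulation added Day 90 only. The separate effect of Day 360 was not estimated.

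**The case against.** The best case for the plan has four parts.

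- **The wording is not airtight.** The sentence in 2.6.2, "LDL-C from baseline over visits (Day 150, 270, 330) as specified for primary endpoint", ends by pointing to the primary endpoint's model, which has five visits. The parenthesis could be read as naming the visits of interest. This stands as an ambiguity, but the same sentence lists three visits, and a programmer would most naturally fit three. One clarifying line is needed either way.
- **Few participants should be affected.** LDL-C results are blinded until Day 360 (Protocol 8.3.1), so a poor Day 90 response is not visible and has no obvious direct route to dropout. Participants who stop treatment remain in follow-up unless consent is withdrawn (Protocol 8 and 9.1.1). An early-exit visit after Day 90 is mapped to Day 150 (SAP Table 2-1), so a leaver with an exit LDL-C does enter the three-visit model. If 50% or 80% of leavers give such a sample (assumed), the bias in the inclisiran mean at 6% dropout and a log-odds slope of 1.0 falls from about 0.7 to about 0.4 or 0.3 points. All of this stands. It shrinks the problem but does not help those who leave without an exit sample.
- **A MAR check that uses Day 90 already exists.** The five-visit MMRM in 2.5.5 covers Day 330. It does not report the time-adjusted average.
- **The inputs are assumed.** The documents give no dropout rate, SD or correlation, so the figures show scale only.

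A reader might infer that the three-visit model always flatters inclisiran, because poor responders leave. The documents do not support that. The analysis compares arms, and the table shows overstatement, understatement and cancellation, depending on who leaves each arm. A reader might also infer that the alpha-controlled test is at risk. It is not, because that test is the imputed analysis of 2.6.2.

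**Conclusion.** The point holds as a small, conditional improvement. As most naturally read, SAP 2.6.4 discards LDL-C values that both the main analysis of this endpoint and the primary endpoint's MMRM use, and its MAR assumption is correspondingly stronger than it needs to be.

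With SD 20, correlation 0.6 and 3% to 10% dropout after Day 90, the between-arm difference shifts by about 0.5 to 3 points in the non-cancelling patterns, in either direction, and by about zero otherwise. These figures assume that leavers supply no later LDL-C, so blinding, continued follow-up and early-exit mapping should make the real shift smaller. Against an effect near 45 points and an SE of about 3.2 (45/3.2 is roughly 14 standard errors), even a 3-point shift would be unlikely to change the test conclusion.

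The stronger reason to act is interpretive: this is the endpoint's one named sensitivity analysis, and it should differ from the main analysis in the missing-data assumption alone.

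**What to change.** In SAP 2.6.4, state that the no-imputation MMRM for the time-adjusted endpoint is fitted to Days 90, 150, 270, 330 and 360, as in 2.5.5, and that the contrast remains the equal-weight average of the Day 150, 270 and 330 treatment differences. In 2.6.2, say explicitly which visits are outcomes in the model and which form the contrast, so that the reference to the primary endpoint's specification has one meaning.

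The cost is a line or two of text and a changed visit list in the program. The data are collected and the five-visit model is already planned for the primary endpoint. In the simulations, adding Day 90 did not increase the standard error.

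The SAP is Amendment 4, reproduced in the study-report appendix, and the Part 1 database lock has passed. If the text can no longer be changed, the five-visit version can be reported as a documented additional run, as was done for the PCSK9 analysis added after that lock.

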2.6.5 Supplementary analyses

Supplementary analyses of key secondary endpoints will be performed in subgroups as specified in Section 2.2.1. The MMRM model (using control-based pattern mixture model for missing value imputation) will be used to evaluate the difference between inclisiran and placebo groups in each subgroup.

Another supplementary analysis for Lp(a) will be applied in log-transformed scale using same MMRM without multiple imputation specified above.

2.7 Analysis of other secondary efficacy objective(s)

Other secondary efficacy endpoints include the percent change and absolute change from baseline throughout the time course up to Day 720 (Year 2) in the following:

- LDL-C
- Apo B
- Lp(a)
- non-HDL-C
- total cholesterol
- triglycerides
- HDL-C
- VLDL-C
- Apo A1
- PCSK9

Descriptive summaries by treatment group and Part and Line-Plot displaying mean will be provided by treatment group and Part for all above endpoints. The overall (Part 1 and Part 2 combined) descriptive summaries and Line-Plot of LDL-C, Apo B, Lp(a), non-HDL-C, total cholesterol and PCSK9 will additionally be provided.

Novartis	For business use only	Page 28
SAP amendment 4		CKJX839C12301

Listings of all the above endpoints for all the available visits, including time-adjusted percent change in LDL-C will be provided. In addition, the absolute change in LDL-C and percent change in LDL-C, Apo B, Lp(a), non-HDL-C, total cholesterol and PCSK9 from baseline to Day 720 (Year 2) will be provided.

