1.2 Purpose

Study CKJX839C12301 (ORION-16) is a pivotal phase III study designed to evaluate safety, tolerability, and efficacy of inclisiran in adolescents (aged 12 to <18 years) with HeFH and LDL-C >130 mg/dL (3.4 mmol/L). The use of inclisiran (as an adjunct to stable, optimal background lipid-lowering therapy) for the treatment of HeFH in adolescent patients who require additional lipid-lowering will be investigated in order to obtain needed pediatric information on inclisiran. The follow-up period (Part 2/Year 2) serves to collect longer-term data on inclisiran and also allows access of study participants to a potentially effective treatment.

2 Objectives and endpoints

Table 2-1 Objectives and related endpoints

Objective(s)	Endpoint(s)	
Primary objective(s)	Endpoint(s) for primary objective(s)	
• The primary objective is to demonstrate superiority of inclisiran compared to placebo in reducing LDL-C [percent change] at Day 330 (Year 1) in adolescents (aged 12 to <18 years) with HeFH and elevated LDL-C	 Percentage change in LDL-C from baseline to Day 330 (Year 1) See Section 2.1 for primary estimand 	
Secondary objective(s)	Endpoint(s) for secondary objective(s)	
Demonstrate superiority of inclisiran compared to placebo in reducing LDL-C [time-adjusted percent change] over Year 1	• Time-adjusted percent change in LDL-C from baseline after Day 90 and up to Day 330 (Year 1)	
Demonstrate superiority of inclisiran compared to placebo in reducing LDL-C [absolute change] at Day 330 (Year 1)	 Absolute change in LDL-C from baseline to Day 330 (Year 1) 	

Objective(s)	Endpoint(s)		
Demonstrate superiority of inclisiran compared to placebo in reducing Apo B, lipoprotein (a) [Lp(a)], non-high density lipoprotein cholesterol (non-HDL-C), and total cholesterol [percent change] at Day 330 (Year 1)	Percent change in Apo B, Lp(a), non-HDL-C, and total cholesterol from baseline to Day 330 (Year 1)		
• Evaluate the effect of inclisiran, compared to placebo (for Year 1) and long-term (up to Day 720), on lowering LDL-C, other lipoprotein and lipid parameters, and PCSK9 over time	 Percent change and absolute change in LDL-C, Apo B, Lp(a), non-HDL-C, total cholesterol, triglycerides, high density lipoprotein cholesterol (HDL-C), very low density lipoprotein cholesterol (VLDL-C), apolipoprotein A1 (Apo A1) and PCSK9 from baseline to each assessment time up to Day 720 (Year 2) 		

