6.4 Treatment blinding

Part 1 (Year 1)

Part 1 of the study is randomized, double-blind and placebo-controlled. Participants, investigator staff, persons performing the assessments, and the clinical trial team (CTT) will remain blind to the identity of the treatment from the time of randomization until at least database lock for all Part 1 (Year 1) data, using the following methods: (1) Randomization data are kept strictly confidential until the time of unblinding, and will not be accessible by anyone else involved in the study with the following exceptions: the independent statistician and programmer who need to have access to prepare interim analysis reports for the DMC and the

Unblinding will occur in the case of participant emergencies and at the conclusion of the study. Unblinding of the CTT and other parties (as needed) will also occur after the Year 1 database lock, which is planned after all participants have completed the Day 360 visit.

Part 2 (Year 2)

Due to the single-arm, open-label design, treatment in Part 2 of the study will be open to participants, investigator staff, persons performing the assessments, and the CTT.

In order to maintain the blind for Part 1 of the study, on the "switch" day (Day 360), participants randomized to placebo in Part 1 will receive blinded inclisiran, while participants randomized to inclisiran in Part 1 will receive blinded placebo.

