12.5 Analysis of secondary endpoints/estimands

12.5.1 Efficacy and/or Pharmacodynamic endpoint(s)

The following are key secondary efficacy endpoints:

- 1. Time-adjusted percent change in LDL-C from baseline after Day 90 and up to Day 330 (Year 1)
- 2. Absolute change in LDL-C from baseline to Day 330 (Year 1)
- 3. Percent change in Apo B from baseline to Day 330 (Year 1)

- 4. Percent change in Lp(a) from baseline to Day 330 (Year 1)
- 5. Percent change in non-HDL-C from baseline to Day 330 (Year 1)
- 6. Percent change in total cholesterol from baseline to Day 330 (Year 1)

A hierarchical testing strategy will be applied to control the family-wise type I error rate at the significance level of 0.025 (one-sided test) to assess superiority of inclisiran over placebo. Hypotheses associated with the key secondary endpoints will be tested in the order listed above. The key secondary endpoints will be analyzed using ANCOVA with imputation performed using the washout model as discussed in Section 12.4.2. Details, including possible sensitivity analyses performed using the MMRM, will be provided in the SAP.

Other secondary efficacy endpoints include the percent change and absolute change from baseline throughout the time course up to Day 720 (Year 2) in the following:

- LDL-C
- Apo B
- Lp(a)
- non-HDL-C
- total cholesterol
- triglycerides
- HDL-C
- VLDL-C
- Apo A1
- PCSK9

Descriptive summaries by treatment group will be presented.

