Appendix 16.1.9 Documentation of statistical methods

History of changes					
Version	Summary of changes				
1.0	Original version				

1 Statistical methods

The planned statistical analysis is described in Section 12 of the clinical study protocol. The most recent version of Statistical Analysis Plan (SAP) is included below.

Two post-hoc analyses were conducted:

1. After Part 1/Year 1 DBL, percentage change in PCSK9 from baseline to Day 330 using ANCOVA with treatment as fixed effect and baseline PCSK9 and baseline age group as covariates, was added, as only descriptive summary statistics of PCSK9 by treatment and visit had been specified in the SAP before the Part 1/Year 1 DBL.

U NOVARTIS

Clinical Development

KJX839/inclisiran

CKJX839C12301

Two part (double-blind inclisiran versus placebo [Year 1] followed by open-label inclisiran [Year 2]) randomized multicenter study to evaluate safety, tolerability, and efficacy of inclisiran in adolescents (12 to less than 18 years) with heterozygous familial hypercholesterolemia and elevated LDL-cholesterol (ORION-16)

Statistical Analysis Plan (SAP)

Author:	Trial statistician
Document type:	SAP Documentation
Document status:	Amendment 4

Release date: 3-Dec-2024

Number of pages: 47

Property of Novartis For business use only May not be used, divulged, published or otherwise disclosed without the consent of Novartis

Novartis				Confidential	Page 3	of 48	
Clinical S	tudy Re	port Appe	ndix 16.1.9, v1.0		Study No. CKJX839C12307		
	Novartis SAP arr	s nendment 4	F	or business use only	Page 2 CKJX839C12301		
	Docun Date	nent Hist Time point	ory – Changes co Reason for update	ompared to previous fin Outcome for update	nal version of SAP Section and title impacted (Current)		
	05- Oct- 2020	Prior to DB lock	Creation of final version	N/A - First version	NA		

Novartis				Confidential	Page	4 of 48
Clinical S	tudy Re	oort Appe	endix 16.1.9, v1.0		Study No. CKJX8390	C12301
	Novartis SAP am	endment 4	F	or business use only	Page 3 CKJX839C12301	
	Date	Time point	Reason for update	Outcome for update	Section and title impacted (Current)	

Novartis				Confidential			Page 5 of 48
Clinical St	udy Re	port Appe	ndix 16.1.9, v1.0			Study No. Ck	JX839C12301
	Novartis SAP an	s nendment 4	F	or business use onl	у	CKJX839	Page 4 C12301
	Date	Time point	Reason for update	Outcome for upd	ate	Section an title impact (Current)	d æd

Novartis				Confidentia	I		Page 6 of 48

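### The Year 1 objective for the other lipids and PCSK9 is a comparison with placebo, but the plan gives no between-arm difference or interval for triglycerides, HDL-C, VLDL-C or Apo A1, and PCSK9 has only a post hoc one

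*SAP*

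**What the plan says.** The protocol's objectives table (Section 2, Table 2-1) includes this secondary objective: "Evaluate the effect of inclisiran, compared to placebo (for Year 1) and long-term (up to Day 720), on lowering LDL-C". It goes on to cover other lipid and lipoprotein parameters and PCSK9 over time. The endpoints are percent and absolute change from baseline at each assessment up to Day 720. SAP Table 1-1 carries the same objective.

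The analysis assigned to it is descriptive in both documents. Protocol 12.5.1 says: "Descriptive summaries by treatment group will be presented". SAP 2.7 says: "Descriptive summaries by treatment group and Part and Line-Plot displaying mean will be provided by treatment group and Part for all above endpoints". It adds listings, and combined Part 1 and Part 2 summaries for some parameters. SAP 2.10 (Biomarkers) only refers back to 2.7.

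The opening page of Appendix 16.1.9, which contains the SAP, records a later addition: "After Part 1/Year 1 DBL, percentage change in PCSK9 from baseline to Day 330 using ANCOVA with treatment as fixed effect", with baseline PCSK9 and age group as covariates. The reason given is: "as only descriptive summary statistics of PCSK9 by treatment and visit had been specified in the SAP before the Part 1/Year 1 DBL".

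**The concern.** The objective names a treatment effect relative to placebo, and Part 1 is randomised and blinded, so that effect can be estimated directly. The analysis attached to the objective stops short of it: no inclisiran-minus-placebo difference and no measure of its uncertainty. A reader has to judge the effect by setting two columns of summaries side by side, without baseline adjustment, without the imputation used for the main endpoints, and with a placebo arm half the size of the active arm.

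PCSK9 matters most here, because it is the protein whose mRNA inclisiran degrades (protocol 1.1). The sponsor later wanted a modelled contrast for it and had to report that contrast as post hoc, which a line in the SAP before the lock would have avoided. The short description of that ANCOVA also does not mention the washout imputation or the separate variances by arm of SAP 2.5.2. Pre-specification would have settled both.

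**Working it through.** The documents give no figure for these endpoints, and the sample-size SDs are redacted, so there is nothing to reproduce. The main check sets objective against analysis.

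**Step 1. Which parameters have a planned between-arm estimate?** Sampling days are from protocol 8.3.1, 8.3.2 and Table 8-1; analyses are from SAP 2.5 to 2.7.

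| Parameter in SAP 2.7 | Post-baseline samples in Year 1 | Between-arm estimate at Day 330 |
|---|---|---|
| LDL-C | Days 90, 150, 270, 330, 360 | Planned: primary (percent), key secondary (absolute) |
| Apo B, Lp(a), non-HDL-C, total cholesterol | Days 150, 330, 360 | Planned: key secondary (percent) |
| Triglycerides, HDL-C, VLDL-C, Apo A1 | Days 150, 330, 360 | None in the visible text |
| PCSK9 | Days 90, 150, 330, 360 | None planned; post hoc ANCOVA |

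So five of ten parameters are covered, four are not, and one is covered only post hoc.

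**Step 2. When was the PCSK9 model added?** The appendix places it after the Part 1/Year 1 database lock. Protocol 6.4 says: "Unblinding of the CTT and other parties (as needed) will also occur after the Year 1 database lock". The post hoc status is stated in the documents. Whether the treatment codes were already open when the model was chosen is not.

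**Step 3. What would the missing estimate look like?** This is an illustration on assumed SDs, taken as equal in the two arms.

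- Inputs: 141 enrolled (SAP 1.1) at 2:1, about 94 and 47; the minimum of 102 gives 68 and 34. Assumed SD of percent change: 15 to 40 points.
- Formula: half-width = 1.96 × SD × √(1/n₁ + 1/n₂).
- N = 141: 1.96 × √(1/94 + 1/47) = 1.96 × 0.1786 = 0.35 SD, or 5.3 points (SD 15) to 14.0 points (SD 40).
- N = 102: 1.96 × √(1/68 + 1/34) = 1.96 × 0.2100 = 0.41 SD, or 6.2 to 16.5 points.

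**Step 4. What does baseline adjustment add?** If r is the correlation between baseline and the change, the standard error is multiplied by √(1 − r²). That is 0.954 at r = 0.3 and 0.866 at r = 0.5, a reduction of 5% to 13%. These values of r are assumed.

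**Step 5. What is the multiplicity price?** If all five parameters were tested on one endpoint each at one-sided 0.025, independently and with no true effects, the chance of at least one false positive would be 1 − 0.975⁵ = 0.119. This is why the intervals should be called nominal and kept outside the hierarchy.

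**The case against.** The strongest reply is that the tiers are deliberate. Table 2-1 sets a superiority aim for the primary and key secondary endpoints and only an evaluation aim for this objective. Protocol 12.5.1 matches the first to ANCOVA with hierarchical testing and the second to descriptive summaries, and the SAP follows it. This stands: no formal test is owed, and the SAP does not depart from the protocol. It does not remove the gap, because evaluating an effect against placebo still calls for an estimate of the difference and its precision.

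Second, Part 1 results are shown by randomised group (SAP 2.1). A reader might infer that the plan offers only before-and-after changes, or that the arms are never compared. The documents do not support that: the columns stand side by side, and any drift common to both arms appears in the placebo column too. If the summaries give n, mean and SD, a reader can compute an unadjusted difference by hand. What is missing is a reported, baseline-adjusted difference with an interval.

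Third, a reader might worry about false positives from within-arm significance tests. SAP 2.7 plans no within-arm test, p-value or interval, so error rates for such tests do not bear on this plan.

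Fourth, the sponsor disclosed the PCSK9 addition, its reason and its post hoc status. That stands. A reader might infer that the model was chosen with the treatment codes in view. The appendix says only that it came after the lock; unblinding by then is an inference from protocol 6.4.

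Last, not all of the text is visible. The appendix states "Two post-hoc analyses were conducted" and the public text shows one of them, so a contrast for another parameter may exist. It would still be post hoc.

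**Conclusion.** The mismatch between objective and analysis is real, and it is in both documents. In the visible text, triglycerides, HDL-C, VLDL-C and Apo A1 have no planned estimate of the Year 1 difference from placebo, and PCSK9 has one only as a post hoc Day 330 ANCOVA. The sponsor's decision to add that ANCOVA shows that descriptive summaries were not enough for at least one of these parameters.

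The consequence is limited. The primary analysis, the key secondary analyses, the sample size and the control of type I error are untouched. What is lost is a direct answer to one stated secondary objective, with its precision: an interval of about ±0.35 SD at 141 participants. The conversion to percentage points rests on assumed SDs and should be read only as a range. The change is worth making because it is cheap, not because any main conclusion is at risk.

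**What to change.** In SAP 2.7, with a matching sentence in protocol 12.5.1:

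- Keep the descriptive summaries and plots.
- For triglycerides, HDL-C, VLDL-C, Apo A1 and PCSK9, report the inclisiran-minus-placebo LS mean difference at Day 330 with a two-sided 95% confidence interval, on the FAS.
- Use the ANCOVA of SAP 2.5.2: treatment, age group, the parameter's own baseline, and separate variances by arm.
- Use the washout imputation of SAP 5.7.1, limited to the visits at which each parameter is measured. Its visit list includes Day 270, when none of the five is sampled, and Day 90, when only PCSK9 is.
- State that the intervals are nominal and outside the hierarchy.
- Label every contrast added after the Part 1 lock as post hoc, as was done for PCSK9.
- Keep Part 2 descriptive, since it has no placebo arm.

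Two options are worth considering. Because the objective is framed over time, the other sampled Year 1 visits could be reported in the same way. A log-scale analysis of triglycerides and VLDL-C would guard against skewness, as SAP 2.6.5 already does for Lp(a).

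The cost is one paragraph and one table from existing code, with no new data. The small downside is a few more nominal intervals without alpha control.
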